### **9.3. Vital Signs**

Vital signs (temperature, heart rate, systolic blood pressure (SBP), diastolic blood pressure (DBP)) will be summarized using descriptive statistics (sample size, mean, SD, median, minimum, and maximum) at baseline and at each post-baseline time point by treatment. Change from baseline will also be summarized at each post-baseline time point. Mean (+/- SD) Vital Sign values will be graphically presented over time by treatment. All vital signs results will be listed.

### **9.4. ECG Results**

Shift from baseline in 12-Lead ECG overall interpretation (results are Normal, Abnormal Not Clinically Significant (NCS), or Abnormal Clinically Significant (CS)) will be summarized at each post-baseline visit by treatment. Mean (+/- SD) continuous ECG parameter values will be graphically presented over time by treatment.

Additionally, the number and percentage of subjects will be summarized for the following QTcF Interval result categories at baseline and each post-baseline visit by treatment:

- <=450 msec (males) or <=470 msec (females)
- >450 msec (males) or >470 msec (females)
- Change from baseline <=60 msec (only applies to Week 4)
- Change from baseline >60 msec (only applies to Week 4)

A listing of ECG results will present the interpretations of abnormalities and whether these are considered clinically significant by the investigator.

### **9.5. Physical Exam**

Physical exam findings will be listed.

## APPENDIX A: PRESENTATION OF DATA AND PROGRAMMING SPECIFICATIONS

### Tables

- Formal organization of tabulations may be changed during programming if appropriate, e.g., tables for the different variables may be combined into a single table, or tables with more than one variable may be split into several tables.
- Means, medians, and quartiles will be presented to one more decimal place than the raw data. SDs will be presented to two more decimal places than the raw data. Minimums and maximums will be reported with the same number of decimal places as the raw data.
- Percentages will be presented to the tenths place.
- For frequency counts of categorical variables, categories whose counts are zero will be displayed for the sake of completeness. For example, if none of the subjects discontinue due to “lost to follow-up,” this reason will be included in the table with a count of 0. Categories with zero counts will not have zero percentages displayed.
- The last footnote will be “Reference: xxx”, where xxx indicates the source listing number(s).

### Listings

- Formal organization of the listing may be changed during programming if appropriate, e.g., additional variables may be included, change in the column order, or the listing may be split into multiple parts due to space constraints, etc.
- If not otherwise specified, all data listings will be sorted by treatment, subject number, visit, and date/time as appropriate.
- All date values will be presented in a ISO 8601 date (e.g., 2001-08-29) format.
- All observed time values will be presented using a 24-hour clock HH:MM:SS format (e.g., 01:35:45 or 11:26). Seconds will only be reported if they were measured as part of the study.

### Missing or incomplete dates, i.e., AEs and concomitant medications

The most conservative approach will be systematically considered. If the AE onset date is missing or incomplete, it is assumed to have occurred during the study treatment phase (i.e., considered a TEAE) except if the partial onset date or other data such as the stop date, indicates differently. Similarly, a medication with partial start and stop dates could be considered as a concomitant treatment.

The following algorithms will be applied to missing and incomplete start and stop dates:

### Start Dates

- If the day portion of the start date is missing, then the start date will be estimated to be equal to the date of IP administration, provided the start month and year are the same as IP administration and the stop date is either after IP administration or completely missing. Otherwise, the missing day portion will be estimated as ‘01’.
- If both the day and month portions of the start date are missing, then the start date will be estimated to be equal to the date of IP administration, provided the start year is the same as IP administration and the stop date is either after IP administration or completely

missing. Otherwise, the event will be assumed to start on the first day of the given year, e.g., 2013-??-?? is estimated as 2013-01-01.

- If the start date is completely missing and the stop date is either after IP administration or completely missing, the start date will be estimated to be the day of IP administration. Otherwise, the start date will be estimated to be the first day of the same year as the stop date. All other non-AE and non-concomitant medication day calculations where only partial dates are available will be handled as follows: the first day of the month will be used in the calculations if the day part of a start date is missing while January 1 will be employed if both the month and day parts of a start date are missing.
- For treatment start dates, if patients are randomized and have non-missing visit data for Week 4 as well as non-missing treatment diary data, then start date is set to earliest treatment diary date. If patient's treatment diary data is missing or Week 4 visit is missing, then treatment start date is set to earliest recorded exposure date. Drug dispensation date is used as treatment start date if no other data is available.

### **Stop Dates**

- If only the day of resolution is unknown, the day will be assumed to be the last of the month, e.g., 2013-01-?? will be treated as 2013-01-31.
- If both the day and month of resolution are unknown, the event will be assumed to have ceased on the last day of the year, e.g., 2013-??-?? will be treated as 2013-12-31.
- If the stop date is completely missing or the event is continuing, the event will be assumed to be after IP administration and will be left as missing.
- For treatment stop dates, if patient has non-missing treatment diary data but has data gaps of more than 3 days, then treatment stop date is set to start date + 28 days. If treatment diary data is non-missing and there are no data gaps of 3 days or more then treatment stop date is set to last treatment diary date. If treatment diary data is missing but patient is recorded to have completed study, then treatment stop date is set to start date + 28 days. Finally, if treatment diary data is missing and patient has not completed the study, then treatment stop date is set to study withdrawal date.

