## 5.2 Packaging and Labeling

Study product will be supplied in kits labeled only with a randomly generated Treatment Kit #. Each kit will contain 28 vials of study drug (sufficient for 28 days of treatment) with each vial containing 7 mL of study drug. Study product will be stored at the University of Pennsylvania Investigational Drug Service. Vials of drug will be provided packaged in a cardboard box and inside amber plastic bags to reduce UV exposure.

Drug product labels are shown below in **Table 5.2-1**. Labels are generated in tandem as shown: one side to be affixed to each Drug Product kit and the second side as detachable for pharmacy logs. As participants present for randomization, treatment assignments will follow the randomization schema in successive order. The study pharmacist will write the Subject ID# and dispensing date on the two labels at the time of study drug dispensation. The side that had been affixed to the Drug Product Kit will remain, while the other half is detached and affixed into the Pharmacy Log form. As noted, the detachable side for Pharmacy is designated as to whether the vials in the kit contain active drug (GLS-1200) or placebo (0.9% saline).

The randomized Treatment Kit # and the designation as Active or Placebo serve as independent confirmatory checks on treatment assignment.

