## **APPENDIX C: TABLE LAYOUTS**

Table 14.1.1.1  
Subject Disposition  
(All Subjects)

Study Site Subject Status	GLS-1200	Placebo	Overall
Overall			
Screened			xx
Screen Failures			xx
ITT Population [1]	xx	xx	xx
Safety Population [2]	x (xx.x%)	x (xx.x%)	x (xx.x%)
PP Population [3]	x (xx.x%)	x (xx.x%)	x (xx.x%)
Completed the study [4]	x (xx.x%)	x (xx.x%)	x (xx.x%)
Discontinued the study	x (xx.x%)	x (xx.x%)	x (xx.x%)
Reason for discontinuation			
<Reason #1>	x (xx.x%)	x (xx.x%)	x (xx.x%)
<Reason #2>	x (xx.x%)	x (xx.x%)	x (xx.x%)
<Reason #3>	x (xx.x%)	x (xx.x%)	x (xx.x%)
Site 101			
.			
.			
Site 108			
.			
.			

Percentages are based on the ITT Population.

[1] The Intent-to-treat (ITT) Population includes all randomized to treatment allocation.

[2] The Safety Population includes all subjects who received at least one dose of study treatment.

[3] The Per-protocol (PP) Population includes all subjects who completed the trial, received  $\geq 90\%$  of the study treatments, and have no significant protocol deviations. Trial completion is defined as either completing Week 4 or meeting the study endpoint of PCR confirmed SARS-CoV-2 infection.

[4] Study completion is defined as completing all visits regardless of drug compliance.

Reference: Listing 16.2.1

Source: \\xx\\xx\\xx\\xx\\xx\\xxxx\\xxxxxxxxxxxx\\xxxx\\xxxx.sas      date      time

**Programming note:** Sort discontinuation reasons by descending overall frequency. List all reasons per CRF page.

Table 14.1.1.2  
Reason for Screen Failure  
(All Screen Failure Subjects)

Study Site	Reason	Overall (xx)
Overall		
<Reason #1>		x (xx.x%)
<Reason #2>		x (xx.x%)
<Reason #3>		x (xx.x%)
Site 101		
<Reason #1>		x (xx.x%)
<Reason #2>		x (xx.x%)
<Reason #3>		x (xx.x%)
Site 108		
<Reason #1>		x (xx.x%)
<Reason #2>		x (xx.x%)
<Reason #3>		x (xx.x%)

Reference: Listing 16.2.3 and Listing 16.2.1

Source: \\xx\\xxx\\xxx\\xxx\\xxxxxx\\xxxxxxxxxxxx\\xxxx\\xxxxx.sas      date      time

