## **APPENDIX E: LISTING LAYOUTS**

Listing 16.2.1  
Subject Disposition

Treatment: GLS-1200, Placebo

Subject ID	Study Site	Informed Consent Date	Randomization Date	ITT Population [1]	Safety Population [2]	PP Population [3]	First Dose Date	Study Completion Status	Study Completion or Discontinuation Date (Study Day)
xxxx	xxxx	yyyy-mm-dd	yyyy-mm-dd	Yes/No	Yes/No	Yes/No	yyyy-mm-dd	xxxxxxxxxx	yyyy-mm-dd (xx)
xxxx	xxxx	yyyy-mm-dd	yyyy-mm-dd	Yes/No	Yes/No	Yes/No	yyyy-mm-dd	xxxxxxxxxx	yyyy-mm-dd (xx)
xxxx	xxxx	yyyy-mm-dd	yyyy-mm-dd	Yes/No	Yes/No	Yes/No	yyyy-mm-dd	xxxxxxxxxx	yyyy-mm-dd (xx)
xxxx	xxxx	yyyy-mm-dd	yyyy-mm-dd	Yes/No	Yes/No	Yes/No	yyyy-mm-dd	xxxxxxxxxx	yyyy-mm-dd (xx)
xxxx	xxxx	yyyy-mm-dd	yyyy-mm-dd	Yes/No	Yes/No	Yes/No	yyyy-mm-dd	xxxxxxxxxx	yyyy-mm-dd (xx)
xxxx	xxxx	yyyy-mm-dd	yyyy-mm-dd	Yes/No	Yes/No	Yes/No	yyyy-mm-dd	xxxxxxxxxx	yyyy-mm-dd (xx)
xxxx	xxxx	yyyy-mm-dd	yyyy-mm-dd	Yes/No	Yes/No	Yes/No	yyyy-mm-dd	xxxxxxxxxx	yyyy-mm-dd (xx)

[1] The Intent-to-treat (ITT) Population includes all randomized to treatment allocation.

[2] The Safety Population includes all subjects who received at least one dose of study treatment.

[3] The Per-protocol (PP) Population includes all subjects who completed the trial, received  $\geq 90\%$  of the study treatments, and have no significant protocol deviations. Trial completion is defined as either completing Week 4 or meeting the study endpoint of PCR confirmed SARS-CoV-2 infection.

Source: \\xx\xx\xxx\xxx\xxx\xxxxx\xxxxxxxxxxxxx\xxx\xxxx.sas

date      time

Listing 16.2.2  
Protocol Deviations

Treatment: GLS-1200, Placebo

Subject ID	Deviation Date (Study Day)	Deviation Category	Description
xxxxxx	yyyy-mm-dd (xx)	Major/Minor	xxxxxx
xxxxxx	yyyy-mm-dd (xx)	Major/Minor	xxxxxx
xxxxxx	yyyy-mm-dd (xx)	Major/Minor	xxxxxx
xxxxxx	yyyy-mm-dd (xx)	Major/Minor	xxxxxx
xxxxxx	yyyy-mm-dd (xx)	Major/Minor	xxxxxx
xxxxxx	yyyy-mm-dd (xx)	Major/Minor	xxxxxx
xxxxxx	yyyy-mm-dd (xx)	Major/Minor	xxxxxx
xxxxxx	yyyy-mm-dd (xx)	Major/Minor	xxxxxx
xxxxxx	yyyy-mm-dd (xx)	Major/Minor	xxxxxx
xxxxxx	yyyy-mm-dd (xx)	Major/Minor	xxxxxx

Source: \\xx\\xx\\xx\\xx\\xxxx\\xxxxxxxxxxxx\\xxxx\\xxxx.sas

date      time

Listing 16.2.3  
Inclusion/Exclusion Criteria

Treatment: GLS-1200, Placebo

Subject ID	All eligibility criteria met	Criterion not met	Criterion Description
xxxxxx	Yes/No	Inclusion xx/Exclusion xx	xxxxxxxx
xxxxxx	Yes/No	Inclusion xx/Exclusion xx	xxxxxxxx
xxxxxx	Yes/No	Inclusion xx/Exclusion xx	xxxxxxxx

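### The treatment stop-date clause for diaries with gaps has no withdrawal check, so an early leaver can be shown with exposure after leaving the study (minor)

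*SAP*

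**What the plan says.** SAP Appendix A, Stop Dates, derives the treatment stop date through four clauses:

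1. Diary present, long gap: "has data gaps of more than 3 days, then treatment stop date is set to start date + 28 days".
2. Diary present, no long gap: if "there are no data gaps of 3 days or more then treatment stop date is set to last treatment diary date".
3. Diary missing, completer: if "patient is recorded to have completed study, then treatment stop date is set to start date + 28 days".
4. Diary missing, non-completer: "if treatment diary data is missing and patient has not completed the study, then treatment stop date is set to study withdrawal date".

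Duration of exposure is defined in SAP 7.6 as last dose date minus first dose date. Footnote 1 of Table 14.1.5, footnote 1 of Listing 16.2.5.1 and the general formula in Appendix A (Standard Calculations) all add 1 to that difference. Standard Calculations also counts the first dose date as Day 0.

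Listing 16.2.1 shows each participant's completion or discontinuation date, so the date needed for a cap is already in the data. Protocol 5.2 supplies a kit of 28 daily vials.

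**The concern.** Completion is checked only in the two clauses where the diary is missing. A participant who withdrew early and left a partial diary with a gap of more than 3 days is treated as if dosing had run to start + 28 days. The same participant with no diary would be stopped at withdrawal, so having more data yields a less plausible date.

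No other text corrects this. The allowance for contrary information at the start of the missing-dates section of Appendix A concerns adverse-event onset and medication dates, not treatment stop dates.

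The situation can arise. Protocol 4.4 foresees voluntary withdrawal with data retained and encourages early leavers to complete the final-visit procedures, and Protocol 6.1.4 includes diary collection among these.

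Safety and tolerability is a primary objective, and duration of exposure is part of its description. For an affected participant, Listing 16.2.5.1 could show a last dose later than the discontinuation date in Listing 16.2.1.

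Two related wording faults sit in the same rule. A gap of exactly 3 days meets neither diary clause. The SAP also does not say whether blank days after the last entry count as a data gap.

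**Working it through.** The plan states no figure to reproduce, because this is a question of rule logic. The inputs are the four stop-date clauses and the two duration formulas above, the Day 0 convention, the 28-vial kit (Protocol 5.2), and the planned arm sizes of 150 and 75 (Protocol synopsis, Table S1).

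**Excess past withdrawal.** Let W be the study day of withdrawal, with W < 28. The gap clause gives a stop on Day 28, and the no-diary non-completer clause gives Day W. The excess is 28 - W days under either duration formula, because the + 1 cancels.

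| W | Stop, gap clause | Stop, no diary | Excess (days) |
|---|---|---|---|
| 7 | Day 28 | Day 7 | 21 |
| 13 | Day 28 | Day 13 | 15 |
| 20 | Day 28 | Day 20 | 8 |
| 27 | Day 28 | Day 27 | 1 |

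**Example.** Diary entries on Days 0-5 and 11-13, blank on Days 6-10, withdrawal on Day 13. The gap is 5 days, so the stop date is Day 28.
- With the + 1 formula, duration is 28 - 0 + 1 = 29 days, against 13 - 0 + 1 = 14 days for the same person with no diary.
- Under SAP 7.6, the durations are 28 and 13 days.

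**Effect on an arm mean.** One such participant at W = 13 adds 15/150 = 0.10 day in the GLS-1200 arm or 15/75 = 0.20 day in the placebo arm.

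**Meaning of a data gap.** Take a participant with daily entries to Day 10 who withdrew on Day 10.
- If only gaps between entries count, clause 2 applies and the stop is Day 10.
- If blank days after the last entry count up to Day 27, there are 27 - 10 = 17 of them. Clause 1 then applies and the stop is Day 28, an excess of 18 days.

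Under the first reading the error reaches only withdrawers with a gap inside the diary. Under the second it reaches nearly every diary-keeping withdrawer who stops more than 3 days before the end.

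**Gap of exactly 3 days.** Clause 1 needs more than 3 days and clause 2 needs fewer than 3. If only gaps between entries count, no clause applies.

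**Duration formula.** Start + 28 gives 28 days under SAP 7.6 and 28 + 1 = 29 days under the table and listing footnotes, against a kit for 28 days.

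**With the cap.** The stop is min(28, W), raised to the last recorded dose if that is later. At W = 7, 13 and 20 this gives Days 7, 13 and 20, or 8, 14 and 21 days with + 1. For W of 28 or more the cap changes nothing, so a participant who missed only Week 6 is not cut.

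**The case against.** The strongest reply concerns consequence. Duration of exposure is descriptive: no test, confidence interval or exposure-adjusted rate uses it. Doses taken and missed are in Table 14.1.5, and Listing 16.2.5.1 adds the number of days with at least one dose, so a reader could notice the mismatch. The diary is routinely collected only at Week 6 (SAP Table 1, footnote 2), and early leavers whose diary never came back fall under the no-diary clause. All of this stands and keeps the point minor.

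A second reply is that the SAP never says the treatment stop date is the date of last dose. Listing 16.2.5.2 holds daily dosing records from which a last dose could be read directly. If it were, the excess exposure and the conflict between listings would not arise for diary keepers. The reading used here is the natural one, but it is an inference.

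Three stronger readings are tempting and are not supported:

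- **Start + 28 is itself wrong and must become start + 27.** Under SAP 7.6, start + 28 gives exactly 28 days, and Protocol 2.1 describes administration from Day 0 through Week 4. The documents show inconsistent formulas, not which one should yield.
- **The no-diary non-completer clause is also defective.** A participant with no diary who finished treatment and left on Day 35 would get 35 + 1 = 36 days only if completion follows note 4 of Table 14.1.1.1 ("Study completion is defined as completing all visits regardless of drug compliance"). Under note 3 ("Trial completion is defined as either completing Week 4 or meeting the study endpoint of PCR confirmed SARS-CoV-2 infection"), which fits the 4-week end of study in SAP 6.3, the same person is a completer and takes start + 28.
- **The safety comparison is biased.** The documents give no withdrawal or gap rates, so neither a total shift nor a difference between arms can be derived.

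**Conclusion.** The gap clause is wrong as written, and the point is minor. A participant with a partial diary and a gap of more than 3 days who withdrew on Day W < 28 is given a stop date 28 - W days after leaving, and no other text prevents it.

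The effect is confined to the duration row of Table 14.1.5 and to the last-dose date and duration in Listing 16.2.5.1. The other results do not use the stop date:
- The primary endpoint rests on PCR results and study status.
- The per-protocol set and compliance rest on recorded doses.
- Treatment-emergent status depends on the first dose.
- Adverse-event percentages count participants.

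The conclusion assumes that the treatment stop date supplies the date of last dose. Its total size is unknown, because it depends on how many early leavers returned a diary with such a gap and on how a data gap is read.

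**What to change.** In SAP Appendix A, Stop Dates:

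1. In the gap clause, for anyone who left the study before the end of the 4-week treatment period, use the earlier of the imputed date and the withdrawal date, but not before the last recorded dose.
2. State whether blank days after the last diary entry count as a data gap.
3. Use one threshold in both diary clauses, so that a gap of exactly 3 days is covered.
4. State which definition of completion (note 3 or note 4 of Table 14.1.1.1) the no-diary clauses use. Those clauses need no other change.

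Use one duration formula in SAP 7.6, Standard Calculations, Table 14.1.5 and Listing 16.2.5.1, and reconcile it with the start + 28 imputation and the 28-day kit. It would also help to say outright whether the treatment stop date is the date of last dose.

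The cost is SAP wording and a small derivation change, with no new data. The downside is that exposure may still be slightly overstated for participants who stopped dosing before they withdrew. The cap also does not reach someone who stops the spray but remains in telephone contact, as the protocol allows for those PCR-positive at enrollment (section on results of the nasopharyngeal swab).

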##### **6.2. Safety Population**

The Safety Population will include all subjects who received at least one dose of study treatment.

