### **7.6. Drug Exposure**

Exposure summaries of duration of exposure, total number of doses taken, and total number of doses missed, will be provided by treatment. Duration of exposure is defined as the date of last dose minus the date of first dose, regardless if any doses were missed in between.

Dosing data collected from treatment diaries will be listed along with any treatment side effects or device issues, and the number of known or suspected exposures to SARS-CoV-2.

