>80%	x (xx.x%)	x (xx.x%)

Site 101

.

Site 108

.

[1] Duration of exposure is defined as the date of last dose minus the date of first dose + 1.

[2] Treatment compliance is defined as the total number of doses taken divided by the total number of planned doses times 100.

Reference: Listing 16.2.5.1 and Listing 16.2.1

Table 14.2.1.1  
Incidence of SARS-CoV-2 Infection by Visit  
(ITT Population)

	GLS-1200 (N=XX)	Placebo (N=XX)	p-value [1]
Treatment Success [2]	x (xx.x%)	x (xx.x%)	
Treatment Failure [3]	x (xx.x%)	x (xx.x%)	
Lost to follow-up	x (xx.x%)	x (xx.x%)	
Required rescue therapy	x (xx.x%)	x (xx.x%)	
Discontinued study prior to completion of Week 4	x (xx.x%)	x (xx.x%)	
Tested positive for SARS-CoV-2 infection at any time up to Week 4	x (xx.x%)	x (xx.x%)	
Had missing PCR result at any visit up to Week 4	x (xx.x%)	x (xx.x%)	
Died	x (xx.x%)	x (xx.x%)	
Week 0 PCR Result			
n	x	x	
Negative	x (xx.x%)	x (xx.x%)	
Positive	x (xx.x%)	x (xx.x%)	
Missing	x (xx.x%)	x (xx.x%)	
Week 2 PCR Result			
n	x	x	
Negative	x (xx.x%)	x (xx.x%)	
Positive	x (xx.x%)	x (xx.x%)	
Missing	x (xx.x%)	x (xx.x%)	
...			

[1] The p-value is calculated using a Fisher's exact test.

[2] Subjects who test negative for SARS-CoV-2 infection at Weeks 2 and 4 are considered treatment successes.

[3] Subjects who met any of the reasons listed are considered treatment failures. Subjects who fail treatment for multiple reasons are counted once for each reason.

Reference: Listing 16.2.6.1

Source: \\xx\\xxx\\xxx\\xxx\\xxxxxx\\xxxxxxxxxxxx\\xxxx\\xxxxx.sas      date      time

**Programming note: Continue for remaining visits. Repeat for Table 14.2.1.2 Incidence of SARS-CoV-2 Infection (PP Population).**

Table 14.2.2  
Incidence of Individual Symptoms and Average Number of Days with Symptoms by Visit Interval  
(ITT Population)

Symptom	GLS-1200 (N=XX)	Placebo (N=XX)
Subjects who reported Body Aches at least once from Day 1 to Week 2	x (xx.x%)	x (xx.x%)
Subjects who reported Body Aches at least once from Week 2 to Week 4	x (xx.x%)	x (xx.x%)
Subjects who reported Body Aches at least once from Week 4 to Week 6	x (xx.x%)	x (xx.x%)
Subjects who reported Body Aches at least once during the overall treatment phase [1]	x (xx.x%)	x (xx.x%)
Number of days subjects reported Body Aches from Day 1 to Week 2		
n	x	x
Mean (SD)	xx.x (xx.xx)	xx.x (xx.xx)
Median	xx.x	xx.x
Min, Max	xx, xx	xx, xx
Number of days subjects reported Body Aches from Week 2 to Week 4		
n	x	x
Mean (SD)	xx.x (xx.xx)	xx.x (xx.xx)

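### SAP Appendix A dates treatment from diary entries rather than doses taken, so duration of exposure is overstated for anyone who stops the spray but keeps the diary

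*SAP*

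**What the plan says.** SAP 7.6 gives the intended quantity: "Duration of exposure is defined as the date of last dose minus the date of first dose, regardless if any doses were missed in between". Footnote 1 of Table 14.1.5 gives it again, one day longer: "Duration of exposure is defined as the date of last dose minus the date of first dose + 1". Listing 16.2.5.1 and the general duration formula under Standard Calculations in Appendix A also add the 1.

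Appendix A then says how the two dates are obtained.

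- **Start.** With the treatment diary and the Week 4 visit both present, "start date is set to earliest treatment diary date". If either is missing, "then treatment start date is set to earliest recorded exposure date". As a last resort, "Drug dispensation date is used as treatment start date if no other data is available".
- **Stop, diary present.** With a gap of more than 3 days, the stop date is start + 28 days. With "no data gaps of 3 days or more then treatment stop date is set to last treatment diary date".
- **Stop, diary missing.** The stop date is start + 28 days for a study completer and the withdrawal date otherwise.

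The treatment diary as laid out in Listing 16.2.5.2 has one dated row per day, with a Yes/No field for each of three doses, comments, and counts of suspected and known SARS-CoV-2 exposures. SAP 6.2 defines the Safety Population as "all subjects who received at least one dose of study treatment".

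**The concern.** A dated diary row is not a dose. The layout allows a row with all three doses marked 'No', and the exposure counts and comments give a participant a reason to keep filling it in. Protocol 4.4 also asks investigators to have participants who leave early complete all assessments. Under Appendix A such a participant has no data gap, so the stop date is the last row rather than the last spray.

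Tolerability is a primary objective (SAP 2.1). The SAP summarises discontinuation of the study, and TEAEs leading to it, but plans no table of discontinuation of treatment. Duration of exposure is therefore the planned summary that should show when spraying stopped. Dose totals alone cannot: 42 of 84 doses is either 14 full days or 28 days at half the planned number.

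**Working it through.** **Planned doses.** Protocol 5.4 supplies 28 vials and 84 syringes, one syringe per administration. 28 days x 3 = 84, which agrees.

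**Example (assumed dosing pattern).** All doses are taken on Days 0-4, then 'No' is recorded each day to Day 27, with no missing rows.

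- Doses taken: 5 x 3 = 15. Doses missed: 84 - 15 = 69. Compliance: 15/84 = 17.9%, in the under-50% category.
- PP status: 90% of 84 is 75.6, so at least 76 doses are needed. The participant is excluded.
- Duration by the Appendix A dates: 27 - 0 = 27 days (7.6), or 27 - 0 + 1 = 28 days (Table 14.1.5).
- Duration by first and last dose taken: 4 - 0 = 4 days, or 4 - 0 + 1 = 5 days.
- Overstatement: 23 days with either formula.

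**Range.** The diary is kept through treatment day 28 (start counted as day 1), with the +1 formula and a fixed denominator of 84:

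| Last day with doses | Doses taken | Missed | Compliance | Duration, Appendix A | Duration, doses taken |
|---|---|---|---|---|---|
| 1 | 3 | 81 | 3.6% | 28 | 1 |
| 5 | 15 | 69 | 17.9% | 28 | 5 |
| 7 | 21 | 63 | 25.0% | 28 | 7 |
| 14 | 42 | 42 | 50.0% | 28 | 14 |
| 20 | 60 | 24 | 71.4% | 28 | 20 |

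Duration does not move with the day of stopping. Doses taken, doses missed and compliance do.

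**Gap of more than 3 days.** The stop is start + 28 whatever was taken. Duration is 28 days by 7.6 and 28 + 1 = 29 days by Table 14.1.5. Full use of a 28-day kit runs from Day 0 to Day 27, which is 28 days with the +1.

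**Gap of exactly 3 days.** The first branch needs more than 3 days, so 3 does not qualify. The second needs no gap of 3 days or more, so 3 does not qualify there either. The remaining branches need a missing diary. The stop date is undefined.

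**Reach of the stop date.** The TEAE definition (SAP 9.1.4.1) has no end-of-treatment cut-off, and the primary endpoint window (SAP 8.1) runs four weeks from treatment initiation. Neither uses the stop date.

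**The case against.** The strongest reply is that the early stop is not hidden. Table 14.1.5 prints doses taken, doses missed and compliance next to duration, all from doses recorded as taken. Listing 16.2.5.1 counts the days on which any dose was taken, and the PP rule works from completed doses. That stands. A reader might infer that such participants are reported as fully treated, but the documents support this only for duration and last-dose date.

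A second reply is that Appendix A introduces its algorithms as applying to missing and incomplete dates, so recorded dose dates would take precedence. That reading does not rescue the branch in question, which is conditioned on diary data being non-missing and free of a qualifying gap. It is also possible that a 'diary date' was meant as a date with a dose. The text does not say so, and a 'data gap' most naturally means missing rows.

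Third, the mechanism depends on the treatment diary form, which is listed in SAP section 1 but not reproduced. All-'No' rows are possible from the listing layout. That participants go on making them after stopping is an assumption. A reader might go further and expect durations of 43 days (Day 42 - Day 0 + 1) because the diary is collected at Week 6. The visit schedule does not say which diary runs that long, so this is not established.

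Fourth, a reader might infer that people who never dosed enter the safety denominator through the dispensation-date default. No section derives Safety Population membership from the imputed start date, and Listing 16.2.1 carries the population flag and the first-dose date in separate columns. Protocol 8.1 in any case defines its safety set as all randomized participants. What remains is narrower: SAP 6.2 requires a dose without saying what counts as evidence of one.

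**Conclusion.** The point holds as an internal conflict in the SAP with a wrong result for one reported quantity. Followed as written, Appendix A gives 28 days of exposure to a participant who keeps the diary to Day 27 but stopped spraying on Day 4, against a correct 5. Any diary with a gap of more than 3 days receives 29 days with the +1 formula. The 3-day boundary is undefined, and 7.6 is one day short of Table 14.1.5, Listing 16.2.5.1 and Standard Calculations.

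The consequence is limited to the description of exposure. Dose counts, compliance and PP status stay correct, and the stop date changes neither TEAE counts nor the Fisher test. The start date does anchor other derivations, such as treatment emergence and Study Day, but Protocol section 3 has dosing begin immediately after randomization, so shifts there should usually be small.

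This rests on three assumptions: diary rows without doses do occur, 'planned doses' is a fixed 84 (the SAP does not define it for early stoppers), and Appendix A is applied literally. The documents give no basis for saying how many participants would be affected.

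**What to change.** 1. Define first and last dose as the first and last diary date with at least one dose marked 'Yes'.
2. Use imputation only where dosing data are missing, meaning no diary or an unrecorded gap, with a single gap cut-off. Set an imputed stop no later than start + 27 days, or study withdrawal if earlier, and flag imputed dates.
3. Use one duration formula, with the +1, in SAP 7.6 and everywhere else.
4. State that a dispensation date alone is not evidence of a dose for the SAP 6.2 Safety Population, and show the number whose dosing is unknown on a separate line.

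The cost is SAP wording and a few lines of derivation code, since the dose-taken fields are already collected. There is a small downside. Where the diary has a gap, the last 'Yes' may slightly understate exposure, and the cap does the same for anyone with an imputed stop who used leftover vials after missed days.
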